7.2.2 Reporting of Pregnancy and Lactation to the Sponsor and to Merck

Although pregnancy and lactation are not considered adverse events, it is the responsibility of investigators or their designees to report any pregnancy or lactation in a subject (spontaneously reported to them), including the pregnancy of a male subject's female partner that occurs during the trial or within 120 days of completing the trial completing the trial, or 30 days following cessation of treatment if the subject initiates new anticancer therapy, whichever is earlier. All subjects and female partners of male subjects who become pregnant must be followed to the completion/termination of the pregnancy. Pregnancy outcomes of spontaneous abortion, missed abortion, benign hydatidiform mole, blighted ovum, fetal death, intrauterine death, miscarriage and stillbirth must be reported as serious events (Important Medical Events). If the pregnancy continues to term, the outcome (health of infant) must also be reported.

Such events must be reported within 24 hours to the Sponsor and within 2 working days to Merck Global Safety. (Attn: Worldwide Product Safety; [contact])

Product: Pembrolizumab
Protocol/Amendment No.: 2016-0343 Amendment 3.4

7.2.3 Immediate Reporting of Adverse Events

7.2.3.1 Serious Adverse Events

An adverse event or suspected adverse reaction is considered “serious” if, in the view of either the investigator or the sponsor, it results in any of the following outcomes:

- Death
- A life-threatening adverse drug experience – any adverse experience that places the patient, in the view of the initial reporter, at immediate risk of death from the adverse experience as it occurred. It does not include an adverse experience that, had it occurred in a more severe form, might have caused death.
- Inpatient hospitalization or prolongation of existing hospitalization
- A persistent or significant incapacity or substantial disruption of the ability to conduct normal life functions.
- A congenital anomaly/birth defect.

Important medical events that may not result in death, be life-threatening, or require hospitalization may be considered a serious adverse drug experience when, based upon appropriate medical judgment, they may jeopardize the patient or subject and may require medical or surgical intervention to prevent one of the outcomes listed in this definition. Examples of such medical events include allergic bronchospasm requiring intensive treatment in an emergency room or at home, blood dyscrasias or convulsions that do not result in inpatient hospitalization, or the development of drug dependency or drug abuse (21 CFR 312.32).

- Important medical events as defined above, may also be considered serious adverse events. Any important medical event can and should be reported as an SAE if deemed appropriate by the Principal Investigator.
- All events occurring during the conduct of a protocol and meeting the definition of a SAE must be reported to the IRB in accordance with the timeframes and procedures outlined in “The University of Texas M. D. Anderson Cancer Center Institutional Review Board Policy for Investigators on Reporting Serious Unanticipated Adverse Events for Drugs and Devices”.

Reporting to FDA:

- **Serious adverse events will be forwarded to FDA according to 21 CFR 312.32.**

It is the responsibility of the PI and the research team to ensure serious adverse events are reported according to the Code of Federal Regulations, Good Clinical Practices, the protocol guidelines, the sponsor’s guidelines, and Institutional Review Board policy.

Product: Pembrolizumab
Protocol/Amendment No.: 2016-0343 Amendment 3.4

- **Note:** In addition to the above criteria, adverse events meeting either of the below criteria, although not serious per ICH definition, are reportable to the Merck in the same timeframe as SAEs to meet certain local requirements. Therefore, these events are considered serious by Merck for collection purposes.
 - Is a new cancer (that is not a condition of the study);
 - Is associated with an overdose.

Refer to Table 6 for additional details regarding each of the above criteria.

For the time period beginning when the consent form is signed until treatment allocation/randomization, any serious adverse event, or follow up to a serious adverse event, including death due to any cause, that occurs to any subject must be reported within 24 hours to the Sponsor and within 2 working days to Merck Global Safety if it causes the subject to be excluded from the trial, or is the result of a protocol-specified intervention, including but not limited to washout or discontinuation of usual therapy, diet, placebo treatment or a procedure.

For the time period beginning at treatment allocation/randomization through 90 days following cessation of treatment, or 30 days following cessation of treatment if the subject initiates new anticancer therapy, whichever is earlier, any serious adverse event, or follow up to a serious adverse event, including death due to any cause whether or not related to the Merck product, must be reported within 24 hours to the Sponsor and within 2 working days to Merck Global Safety.

Additionally, any serious adverse event, considered by an investigator who is a qualified physician to be related to Merck product that is brought to the attention of the investigator at any time following consent through the end of the specified safety follow-up period specified in the paragraph above, or at any time outside of the time period specified in the previous paragraph also must be reported immediately to the Sponsor and to Merck Global Safety.

All subjects with serious adverse events must be followed up for outcome.

SAE reports and any other relevant safety information are to be forwarded to the Merck Global Safety [contact]

A copy of all 15 Day Reports and Annual Progress Reports is submitted as required by FDA, European Union (EU), Pharmaceutical and Medical Devices agency (PMDA) or other local regulators. Investigators will cross reference this submission according to local regulations to the Merck Investigational Compound Number (IND, CSA, etc.) at the time of submission.

Additionally investigators will submit a copy of these reports to Merck & Co., Inc. (Attn: Worldwide Product Safety; [contact]) at the time of submission to FDA.

7.2.3.2 Events of Clinical Interest

Selected non-serious and serious adverse events are also known as Events of Clinical Interest (ECI) and must be reported within 24 hours to the Sponsor and within 2 working days to Merck Global Safety. (Attn: Worldwide Product Safety; [contact]).

For the time period beginning when the consent form is signed until treatment allocation/randomization, any ECI, or follow up to an ECI, that occurs to any subject must be reported within 24 hours to the Sponsor and within 2 working days to Merck Global Safety if it causes the subject to be excluded from the trial, or is the result of a protocol-specified intervention, including but not limited to washout or discontinuation of usual therapy, diet, placebo treatment or a procedure.

For the time period beginning at treatment allocation/randomization through 90 days following cessation of treatment, or 30 days following cessation of treatment if the subject initiates new anticancer therapy, whichever is earlier, any ECI, or follow up to an ECI, whether or not related to Merck product, must be reported within 24 hours to the Sponsor and within 24 hours to Merck Global Safety.

Events of clinical interest for this trial include:

1. an overdose of Merck product, as defined in Section 7.2.1 - Definition of an Overdose for This Protocol and Reporting of Overdose to the Sponsor, that is not associated with clinical symptoms or abnormal laboratory results.
2. an elevated AST or ALT lab value that is greater than or equal to 3X the upper limit of normal and an elevated total bilirubin lab value that is greater than or equal to 2X the upper limit of normal and, at the same time, an alkaline phosphatase lab value that is less than 2X the upper limit of normal, as determined by way of protocol-specified laboratory testing or unscheduled laboratory testing.*

***Note:** These criteria are based upon available regulatory guidance documents. The purpose of the criteria is to specify a threshold of abnormal hepatic tests that may require an additional evaluation for an underlying etiology.

7.2.4 Evaluating Adverse Events

An investigator who is a qualified physician will evaluate all adverse events according to the NCI Common Terminology for Adverse Events (CTCAE), version 4.0. Any adverse event which changes CTCAE grade over the course of a given episode will have each change of grade recorded in PDMS/CORe.

All adverse events regardless of CTCAE grade must also be evaluated for seriousness.

Table 7 Evaluating Adverse Events

An investigator who is a qualified physician, will evaluate all adverse events as to:

V4.0 CTCAE Grading	Grade 1	Mild; asymptomatic or mild symptoms; clinical or diagnostic observations only; intervention not indicated.
Grade 2	Moderate; minimal, local or noninvasive intervention indicated; limiting age-appropriate instrumental ADL.	
Grade 3	Severe or medically significant but not immediately life-threatening; hospitalization or prolongation or hospitalization indicated; disabling; limiting self-care ADL.	
Grade 4	Life threatening consequences; urgent intervention indicated.	
Grade 5	Death related to AE	
Seriousness	A serious adverse event is any adverse event occurring at any dose or during any use of Merck product that: 
 †Results in death; or †Is life threatening; or places the subject, in the view of the investigator, at immediate risk of death from the event as it occurred (Note: This does not include an adverse event that, had it occurred in a more severe form, might have caused death.); or †Results in a persistent or significant disability/incapacity (substantial disruption of one's ability to conduct normal life functions); or †Results in or prolongs an existing inpatient hospitalization (hospitalization is defined as an inpatient admission, regardless of length of stay, even if the hospitalization is a precautionary measure for continued observation. (Note: Hospitalization for an elective procedure to treat a preexisting condition that has not worsened is not a serious adverse event. A pre-existing condition is a clinical condition that is diagnosed prior to the use of a Merck product and is documented in the patient's medical history.); or †Is a congenital anomaly/birth defect (in offspring of subject taking the product regardless of time to diagnosis); or Is a new cancer; (that is not a condition of the study) (although not serious per ICH definition, is reportable to the Sponsor within 24 hours and to Merck within 2 working days to meet certain local requirements); or Is an overdose (whether accidental or intentional). Any adverse event associated with an overdose is considered a serious adverse event for collection purposes. An overdose that is not associated with an adverse event is considered a 	

		non-serious event of clinical interest and must be reported within 24 hours to the Sponsor and to Merck within 2 working days.
		Other important medical events that may not result in death, not be life threatening, or not require hospitalization may be considered a serious adverse event when, based upon appropriate medical judgment, the event may jeopardize the subject and may require medical or surgical intervention to prevent one of the outcomes listed previously (designated above by a †).
Duration		Record the start and stop dates of the adverse event. If less than 1 day, indicate the appropriate length of time and units
Action taken		Did the adverse event cause Merck product to be discontinued?
Relationship to test drug		Did Merck product cause the adverse event? The determination of the likelihood that Merck product caused the adverse event will be provided by an investigator who is a qualified physician. The investigator's signed/dated initials on the source document or worksheet that supports the causality noted on the AF form, ensures that a medically qualified assessment of causality was done. This initialed document must be retained for the required regulatory time frame. The criteria below are intended as reference guidelines to assist the investigator in assessing the likelihood of a relationship between the test drug and the adverse event based upon the available information.
		The following components are to be used to assess the relationship between Merck product and the AE; the greater the correlation with the components and their respective elements (in number and/or intensity), the more likely Merck product caused the adverse event (AE):
Exposure		Is there evidence that the subject was actually exposed to Merck product such as: reliable history, acceptable compliance assessment (pill count, diary, etc.), expected pharmacologic effect, or measurement of drug/metabolite in bodily specimen?
Time Course		Did the AE follow in a reasonable temporal sequence from administration of Merck product? Is the time of onset of the AE compatible with a drug-induced effect (applies to trials with investigational medicinal product)?
Likely Cause		Is the AE not reasonably explained by another etiology such as underlying disease, other drug(s)/vaccine(s), or other host or environmental factors

Relationship to Merck product (continued)		The following components are to be used to assess the relationship between the test drug and the AE:
Dechallenge	Was Merck product discontinued or dose/exposure/frequency reduced? If yes, did the AE resolve or improve? If yes, this is a positive dechallenge. If no, this is a negative dechallenge.	(Note: This criterion is not applicable if: (1) the AE resulted in death or permanent disability; (2) the AE resolved/improved despite continuation of the Sponsor's product; or (3) the trial is a single-dose drug trial); or (4) Sponsor's product(s) is/are only used one time.)
Rechallenge	Was the subject re-exposed to Merck product in this study? If yes, did the AE recur or worsen? If yes, this is a positive rechallenge. If no, this is a negative rechallenge.	(Note: This criterion is not applicable if: (1) the initial AE resulted in death or permanent disability, or (2) the trial is a single-dose drug trial); or (3) Sponsor's product(s) is/are used only one time). NOTE: IF A RECHALLENGE IS PLANNED FOR AN ADVERSE EVENT WHICH WAS SERIOUS AND WHICH MAY HAVE BEEN CAUSED BY THE MERCK PRODUCT, OR IF REEXPOSURE TO THE MERCK PRODUCT POSES ADDITIONAL POTENTIAL SIGNIFICANT RISK TO THE SUBJECT, THEN THE RECHALLENGE MUST BE APPROVED IN ADVANCE BY THE U.S. CLINICAL MONITOR AS PER DOSE MODIFICATION GUIDELINES IN THE PROTOCOL.
Consistency with Trial Treatment Profile	Is the clinical/pathological presentation of the AE consistent with previous knowledge regarding Merck product or drug class pharmacology or toxicology?	
Record one of the following	The assessment of relationship will be reported in PDMS/CORe by an investigator who is a qualified physician according to his/her best clinical judgment, including consideration of the above elements. Use the following scale of criteria as guidance (not all criteria must be present to be indicative of a Merck product relationship).	

Yes, there is a reasonable possibility of Merck product relationship.	There is evidence of exposure to the Merck product. The temporal sequence of the AE onset relative to the administration of the Merck product is reasonable. The AE is more likely explained by the Merck product than by another cause.
No, there is not a reasonable possibility Merck product relationship	Subject did not receive the Merck product OR temporal sequence of the AE onset relative to administration of the Merck product is not reasonable OR there is another obvious cause of the AE. (Also entered for a subject with overdose without an associated AE.)

7.2.5 Sponsor Responsibility for Reporting Adverse Events

All Adverse Events will be reported to regulatory authorities, IRB/IECs and investigators in accordance with all applicable global laws and regulations.

8.0 STATISTICAL ANALYSIS PLAN

8.1 Statistical Analysis Plan Summary

This is a Phase II open-label study designed to evaluate the safety and efficacy of the combination of MK3475 and 5-azacitidine in patients with MDS. Two different patient groups (hypomethylating failure group and previously untreated MDS group) will be studied. Each cohort will be composed of N=20 patients. Accrual will be parallel for each patient group.

The primary efficacy outcome for each cohort is the overall response rate (ORR) defined as CR + PR + hematological improvement (HI). Overall response will be assessed after 6 cycles of treatment; cycle length is 28 days. A maximum of 20 patients will be enrolled in each cohort (total for study N=40).

Hypomethylating failure MDS cohort

The target ORR with the experimental treatment is 20%. There is no standard treatment for this patient population, we use a null ORR of 5%. The regimen of the experimental treatment will be considered worthy of further investigation if it elicits an increase in ORR to 20% with acceptable toxicity. A >30% therapy related non-hematological grade 3/4 toxicity rate is considered unacceptable. Thus, interim monitoring rules, assuming the prior distributions below, were constructed that meet the following two conditions,

- 1) Stop if $\text{Prob}\{p(\text{ORR}, E) < p(\text{ORR}, H) + 0.15 \mid \text{data}\} > 0.99$, or
- 2) Stop if $\text{Prob}\{p(\text{TOX}, E) > 0.30 \mid \text{data}\} > 0.95$,

where $p(\text{ORR}, E)$ and $p(\text{TOX}, E)$ are the true ORR and toxicity rates for the combination treatment, and $p(\text{ORR}, H)$ is the true ORR rate of the standard treatment. The first rule provides for stopping the study if the data suggest that it is unlikely (i.e., probability < 1%) that ORR rate of the experimental treatment is greater than the ORR rate of standard treatment by 15%. The second condition will stop the study early if excessive therapy-related non-hematological grade 3/4 toxicity (>30%) is highly probable (i.e., probability >95%) for the experimental treatment. Monitoring for toxicity and futility will start with the first patient, and cohort size of 5.

The monitoring rule for the toxicity rate, based on these assumptions and monitoring conditions above is found in Table 8. For example, accrual will cease if 4 or more patients experience toxicities among the first 5 patients.

Table 8. Stop accrual if the number of drug-related non-hematological grade 3/4 toxicities is greater than or equal to indicated (i.e., # patients with toxicities) among the number of patients evaluated				
# patients evaluated	5	10	15	20
# patients with toxicities	4-5	6-10	8-15	Always stop

Monitoring the ORR rate, based on the above assumptions and monitoring conditions is found in Table 9. For example, accrual will cease if no patients experience an overall response within 6 cycles in the first 10 patients treated.

Table 9. Stop accrual if the number with response is less than or equal to indicated (i.e., # patients with overall response) among the number of patients evaluated			
# patients evaluated	5	10-15	20
# patients with response	Never	0	Always stop

Multc Lean Desktop (version 2.1.0) was used to generate the toxicity and futility stopping boundaries and the OC table (Table 10). In order to utilize the software for the design, a response constant rate of 5% and beta (0.1, 1.9) prior were assumed for the standard treatment response rate and experimental treatment response prior distribution, respectively. A delta 15% was assumed. In addition, a 30% toxicity constant rate and beta (0.6, 1.4) priors were assumed for the standard treatment toxicity rate and experimental treatment toxicity prior distribution, respectively.

The probability of stopping the study early if the true ORR of the combination treatment was 20% and the true toxicity rate was 30% was 18%. Probabilities of stopping early for high true toxicity rates (i.e., 50%) were 82% when the true ORR was 5% and 61% when true ORR rate was 20%.

Table 10. Operating characteristics for simultaneous monitoring response and toxicity rates for patients treated with combination treatment		
True Toxicity Rate	True ORR	Prob(stop the trial early)
0.10	0.05	0.5990
	0.10	0.3491
	0.15	0.1973
	0.20	0.1079
	0.25	0.0569

Table 10. Operating characteristics for simultaneous monitoring response and toxicity rates for patients treated with combination treatment

True Toxicity Rate	True ORR	Prob(stop the trial early)
0.20	0.05	0.6040
	0.10	0.3573
	0.15	0.2075
	0.20	0.1192
	0.25	0.0688
0.30	0.05	0.6326
	0.10	0.4037
	0.15	0.2647
	0.20	0.1828
	0.25	0.1360
0.40	0.05	0.7085
	0.10	0.5268
	0.15	0.4166
	0.20	0.3516
	0.25	0.3145
0.50	0.05	0.8230
	0.10	0.7126
	0.15	0.6456
	0.20	0.6062
	0.25	0.5836

Previously untreated MDS cohort

The target ORR with the experimental treatment is 70%, assuming the standard treatment ORR is 50%. The regimen of the experimental treatment will be considered worthy of further investigation if it elicits an increase in ORR to 70% with acceptable toxicity. A >30% therapy related non-hematological grade 3/4 toxicity rate is considered unacceptable. Thus, interim monitoring rules, assuming the prior distributions below, were constructed that meet the following two conditions,

- 3) Stop if $\text{Prob}\{p(\text{ORR}, E) < p(\text{ORR}, H) + 0.20 \mid \text{data}\} > 0.95$, or
- 4) Stop if $\text{Prob}\{p(\text{TOX}, E) > 0.30 \mid \text{data}\} > 0.95$,

where $p(\text{ORR}, E)$ and $p(\text{TOX}, E)$ are the true ORR and toxicity rates for the combination treatment, and $p(\text{ORR}, H)$ is the true ORR rate of the standard treatment. The first rule provides for stopping the study if the data suggest that it is unlikely (i.e., probability < 5%) that ORR rate of the experimental treatment is greater than the ORR rate of standard treatment by 20%. The second condition will stop the study early if excessive therapy-related

non-hematological grade 3/4 toxicity (>30%) is highly probable (i.e., probability >95%) for the experimental treatment. Monitoring for toxicity and futility will start with the first patient, and cohort size of 5.

The monitoring rule for the toxicity rate, based on these assumptions and monitoring conditions above is found in Table 11. For example, accrual will cease if 4 or more patients experience toxicities among the first 5 patients.

Table 11. Stop accrual if the number of drug-related non-hematological grade 3/4 toxicities is greater than or equal to indicated (i.e., # patients with toxicities) among the number of patients evaluated

# patients evaluated	5	10	15	20
# patients with toxicities	4-5	6-10	8-15	Always stop

Monitoring the ORR rate, based on the above assumptions and monitoring conditions is found in Table 12. For example, accrual will cease if 1 patients experience an overall response within 6 cycles in the first 5 patients treated.

Table 12. Stop accrual if the number with response is less than or equal to indicated (i.e., # patients with overall response) among the number of patients evaluated

# patients evaluated	5	10	15	20
# patients with response	0-1	0-4	0-7	Always stop

Multc Lean Desktop (version 2.1.0) was used to generate the toxicity and futility stopping boundaries and the OC table (Table 13) In order to utilize the software for the design, a response constant rate of 50% and beta (1.0, 1.0) priors were assumed for the standard treatment response rate and experimental treatment response prior distribution, respectively. A delta 20% was assumed. In addition, a 30% toxicity constant rate and beta (0.6, 1.4) priors were assumed for the standard treatment toxicity rate and experimental treatment toxicity prior distribution, respectively.

The probability of stopping the study early if the true ORR of the experimental treatment was 70% and the true toxicity rate was 30% was 16%. Probabilities of stopping early for high true toxicity rates (i.e., 50%) were 81% when the true ORR was 50%, and 60% when true ORR rate was 70%.

Table 13. Operating characteristics for simultaneous monitoring response and toxicity rates for patients treated with combination treatment

True Toxicity Rate	True ORR	Prob(stop the trial early)
0.10	0.50	0.5590
	0.60	0.2740
	0.70	0.0850

Table 13. Operating characteristics for simultaneous monitoring response and toxicity rates for patients treated with combination treatment

True Toxicity Rate	True ORR	Prob(stop the trial early)
	0.80	0.0138
	0.90	0.0012
0.20	0.50	0.5646
	0.60	0.2831
	0.70	0.0965
	0.80	0.0262
	0.90	0.0138
0.30	0.50	0.5960
	0.60	0.3349
	0.70	0.1618
	0.80	0.0965
	0.90	0.0850
0.40	0.50	0.6795
	0.60	0.4723
	0.70	0.3349
	0.80	0.2831
	0.90	0.2740
0.50	0.50	0.8053
	0.60	0.6795
	0.70	0.5960
	0.80	0.5646
	0.90	0.5590

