5.10 Clinical Criteria for Early Trial Termination

Early trial termination will be the result of the criteria specified below:

1. Quality or quantity of data recording is inaccurate or incomplete
2. Poor adherence to protocol and regulatory requirements
3. Incidence or severity of adverse drug reaction in this or other studies indicates a potential health hazard to subjects
4. Plans to modify or discontinue the development of the study drug

In the event of Merck decision to no longer supply study drug, ample notification will be provided so that appropriate adjustments to subject treatment can be made.

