8.2 Statistical Analysis Plan

Statistical Analysis Plan

All patients who received any dose of the study agent will be included in the analysis for efficacy and safety. Drop out of patients will count as failure for the efficacy analysis. Demographic/clinical characteristics (i.e. including duration of response) and safety data of the patients will be summarized using descriptive statistics such as mean, standard deviation, median and range. For the primary efficacy analysis, we will estimate the ORR (cohort 1) and ORR (cohort 2) for the combination treatment, along with the 95% credible interval. For the efficacy of cohort 1, a sample size of 20 patients ensures a posterior 95% credible interval for ORR of (0.06, 0.37), if the trial is not terminated early, under the assumption of a 20% ORR. For the efficacy of cohort 2, a sample size of 20 patients ensures a posterior 95% credible interval for ORR of (0.48, 0.85), if the trial is not terminated early, under the assumption of a 70% ORR. The association between ORR and patient's clinical characteristics will be

Product: MK-3475

60

Protocol/Amendment No.: 2016-0343 Amendment 2

examined by Wilcoxon's rank sum test or Fisher's exact test, as appropriate. Toxicity type, severity and attribution will be summarized for each patient using frequency tables. The distribution of time-to-event endpoints (EFS and OS) will be estimated using the method of Kaplan and Meier. Comparisons of time-to-event endpoints by important subgroups will be made using the log-rank tests. Paired t-tests will be used to determine the immunological and molecular changes in the peripheral blood and bone marrow from baseline to the time of response, and to the time of disease progression.

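### The toxicity stopping rule in both cohorts counts only grade 3/4 events, so a patient whose only qualifying event is a treatment-related death (grade 5) is not counted

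*Combined protocol and SAP*

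**What the plan says.** Section 8.1 sets the same toxicity rule for the hypomethylating-agent (HMA) failure cohort and the previously untreated cohort. The threshold sentence in each reads "A >30% therapy related non-hematological grade 3/4 toxicity rate is considered unacceptable". The explanation of the second stopping condition repeats grade 3/4 and requires that excess toxicity be "highly probable (i.e., probability >95%) for the experimental treatment". The captions of Tables 8 and 11 carry the definition into the boundary: "Stop accrual if the number of drug-related non-hematological grade 3/4 toxicities is greater than or equal to indicated". The boundaries are 4 of 5, 6 of 10 and 8 of 15.

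Section 7.2.4 grades events by CTCAE version 4.0. Its Table 7 lists grade 5 separately, as "Death related to AE". No section adds grade 5 to the monitored event, writes the event as grade 3 or higher, or sets a numeric rule for deaths.

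Three other provisions bear on the point:

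- Section 7.2.4: "Any adverse event which changes CTCAE grade over the course of a given episode will have each change of grade recorded".
- Section 8.2: "Drop out of patients will count as failure for the efficacy analysis".
- Section 5.10 lists as a ground for ending the trial: "Incidence or severity of adverse drug reaction in this or other studies indicates a potential health hazard to subjects".

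**The concern.** Safety of the combination is the first primary objective (section 3.1), and this boundary is the only numeric safety stop. As written, the most severe related outcome is the one grade above 2 that does not enter it. With 20 patients per cohort and looks at 5, 10 and 15, a single patient can decide a look. If that patient's only qualifying event is a treatment-related death, the rule says continue where the same number of grade 3/4 patients would say stop. Whether accrual stops then rests on judgement under section 5.10. Settling the reading after such a death has occurred would mean interpreting a stopping rule with the data in hand.

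**Working it through.** **Inputs (section 8.1).** Toxicity prior: "a 30% toxicity constant rate and beta (0.6, 1.4) priors were assumed". Stop if the posterior probability of a toxicity rate above 0.30 exceeds 0.95. Looks at n = 5, 10 and 15. Futility stops: HMA failure, 0 responders at 10 or 15 (Table 9); untreated, at most 1 of 5, 4 of 10 or 7 of 15 (Table 12).

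**Step 1: reproduce the boundaries.** With x counted patients among n, the posterior is Beta(0.6 + x, 1.4 + n − x). The boundary is the smallest x with P(rate > 0.30) > 0.95.

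| n | One below boundary | Posterior | At boundary | Posterior |
|---|---|---|---|---|
| 5 | 3 | 0.8745 | 4 | 0.9751 |
| 10 | 5 | 0.8798 | 6 | 0.9625 |
| 15 | 7 | 0.8927 | 8 | 0.9597 |

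This matches Tables 8 and 11. It also shows the decision effect: if one of the 4, 6 or 8 patients had only a grade 5 event, the literal count moves to the left-hand column and accrual continues.

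**Step 2: reproduce the operating characteristics.** Take exact binomial recursion over the three looks, with response and toxicity independent: P(stop) = 1 − P(no toxicity stop) × P(no futility stop). All 50 entries of Tables 10 and 13 are recovered to within 0.0001. Examples are 0.6062 at toxicity 50% and ORR 20% (Table 10), and 0.5960 at toxicity 50% and ORR 70% (Table 13).

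**Step 3: effect on the toxicity rule alone.** The documents give no rate of fatal toxicity, so 1, 2, 5 and 10 percentage points of grade-5-only patients are assumed. The literal rule sees the true grade 3–5 rate minus those points (for example 0.50 − 0.02 = 0.48).

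| True grade 3–5 rate | Grade 5 counted | 1 point uncounted | 2 points | 5 points | 10 points |
|---|---|---|---|---|---|
| 50% | 0.559 | 0.529 | 0.499 | 0.410 | 0.274 |
| 40% | 0.274 | 0.249 | 0.226 | 0.163 | 0.084 |

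**Step 4: toxicity and futility rules together.** Grade-5-only patients are non-responders. All other patients respond at 20% (HMA failure) or 70% (untreated), independently of toxicity. The true grade 3–5 rate is 50%. Early-stop probabilities, grade 5 counted vs not counted:

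| Grade-5-only points | HMA failure | Untreated |
|---|---|---|
| 1 | 0.607 vs 0.581 | 0.599 vs 0.574 |
| 2 | 0.608 vs 0.556 | 0.602 vs 0.553 |
| 5 | 0.611 vs 0.484 | 0.612 vs 0.496 |
| 10 | 0.616 vs 0.376 | 0.632 vs 0.432 |

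The futility rule therefore recovers little at 1 or 2 points. In the HMA-failure cohort it never stops at 5 patients, and a single responder among the first 10 disables it at both later looks.

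**The case against.** The affected group is narrow. A patient is missed only if the fatal event has no recorded grade 3 or 4 stage and the patient has no other related non-hematological grade 3/4 event. Because every grade change is recorded, many fatal toxicities would be counted before death. This stands, and it is why the point is limited to grade-5-only patients. A death first reported as fatal is still missed.

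One such patient changes the decision only when the count is exactly one below the boundary. The 50% scenario is also near the worst case: for 1 uncounted point, the toxicity-rule loss is 0.012 at a 30% total rate, 0.025 at 40%, 0.030 at 50% and 0.021 at 60%. The 5- and 10-point cases have no support in the documents. All of this stands, and it limits the average effect without touching the decision at the margin.

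Deaths must reach the sponsor within 24 hours (section 7.2.3.1), and section 5.10 permits termination. Both are true, but neither changes the count or sets a threshold. The futility backstop is weaker than it looks, because section 8.2 speaks of dropout in the efficacy analysis and does not mention death or the interim count. Treating a death as an interim non-response is an inference.

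Grade 3/4 may be shorthand for grade 3 or higher. If so, the edit only records the intent.

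Finally, the 30% limit and the prior (mean 0.6/2.0 = 0.30) were stated for grade 3/4 events, so widening the event extends what is called unacceptable. That stands, and the sponsor should confirm it.

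**Conclusion.** The concern holds. In both cohorts the monitored event excludes grade 5, and no other provision puts a grade-5-only patient into the toxicity count. At 3 of 5, 5 of 10 or 7 of 15 counted patients, one additional treatment-related, non-hematological death with no recorded grade 3/4 event would be left out, and the rule would say continue where full counting says stop.

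The average effect is modest if such deaths are rare. At a true grade 3–5 rate of 50% with 1 or 2 grade-5-only points, the loss in stop probability is about 3 to 6 percentage points for the toxicity rule alone (0.559 − 0.529 = 0.030; 0.559 − 0.499 = 0.060). With futility included it is about 2.5 to 5 points. It is large only if such deaths are frequent. These figures rest on assumed grade-5-only rates and, for the joint results, on response being independent of toxicity in the remaining patients.

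The printed boundaries and operating characteristics are correct for whatever event is counted. Only the event definition is at fault. It should be fixed because it concerns the only numeric safety stop and the repair is cheap. The toxicity appendix cited in section 4.2.4.2 is not among the documents, and the stopping rule does not refer to it.

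**What to change.** In both cohort paragraphs of section 8.1, replace grade 3/4 with grade 3 or higher, including treatment-related death (grade 5). Make the change in the threshold sentence, in the explanation of the second stopping condition, and in the captions of Tables 8 and 11. The sponsor should confirm in the same edit that the 30% limit is meant for this wider event.

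The boundaries and Tables 10 and 13 stand, because they are indexed by the rate of the counted event. The cost is a few words and slightly more frequent stopping. With a 30% grade 3/4 rate plus 1 or 2 points of grade-5-only events, the toxicity rule's stop probability rises from 0.084 to 0.098 or 0.112. With a 20% rate it rises from 0.013 to 0.017 or 0.021.
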